 - The screening period may be extended (but cannot exceed 8 weeks) for patients who have used systemic corticosteroids for their MS before screening.
- Previous or concurrent treatment with any investigational agent or treatment with any experimental procedure for MS (e.g., treatment for chronic cerebrospinal venous insufficiency)
- Certain laboratory abnormalities or findings at screening, including the following:
 - Positive serum β-hCG
 - Positive for hepatitis B (hepatitis B surface antigen [HBsAg] positive or hepatitis B core antibody [total HBcAb] confirmed by positive viral DNA polymerase chain reaction [PCR]) or hepatitis C (HepCAb)
 - AST or ALT ≥ 2.0 upper limit of normal
 - Platelet count < 100,000/µL (< 100 × 10⁹/L)
 - ANC < 1.5 × 10³/µL
 - Abnormal lymphocyte count (below lower level of normal)

Re-testing before baseline: in rare cases in which the screening laboratory samples are rejected by the laboratory (e.g., hemolyzed sample) or the results are not assessable (e.g., indeterminate) or abnormal, the tests need to be repeated. Any abnormal screening laboratory value that is clinically relevant should be retested in order to rule out any progressive or uncontrolled underlying condition. The last value before randomization must meet study criteria. In such circumstances, the screening period may need to be prolonged but should not exceed 8 weeks.

- Inability to complete an MRI (contraindications for MRI include but are not restricted to weight ≥ 140 kg, pacemaker, cochlear implants, intracranial vascular clips, surgery within 6 weeks of entry into the study, coronary stent implanted within 8 weeks prior to the time of the intended MRI, contraindication to gadolinium, etc.)
- Lack of peripheral venous access
- Pregnant or lactating, or intending to become pregnant during the study
 - Women of childbearing potential must have a negative serum *or urine* pregnancy test result within 14 days prior to initiation of study drug.

Exclusion Criteria Specific to RMS Patients

- Diagnosis of PPMS or secondary progressive multiple sclerosis without relapses

End of Study

The end of this study is defined as the date when the last patient, last visit (LPLV) occurs or the date at which the last data point required for statistical analysis or safety follow-up is received from the last patient, whichever occurs later.

Length of Study

The total length of the study is expected to be approximately 6.5 years from the first patient enrolled to LPLV.

Investigational Medicinal Products

Test Product (Investigational Drug)

The investigational medicinal product for this study is ocrelizumab.

Non-Investigational Medicinal Products

Premedicate with 100 mg of methylprednisolone (or an equivalent) approximately 30 minutes prior to each ocrelizumab infusion *and with an antihistaminic drug (e.g., diphenhydramine) approximately 30 – 60 minutes before each infusion of ocrelizumab* to reduce the frequency and severity of infusion-related reactions (IRRs).

The addition of an antipyretic (e.g., acetaminophen/paracetamol) may also be considered *to further reduce the frequency and severity of IRRs*.

Statistical Methods

Statistical analyses will be performed on the analysis population, defined as all enrolled patients who received at least one infusion of ocrelizumab, even if the infusion was incomplete.

Primary Endpoints

Primary endpoints for the RMS cohort include:

- Change in levels of NfL in CSF from treatment baseline to post-treatment with ocrelizumab
- Change in number of CD19+ B cells in CSF from treatment baseline to post-treatment with ocrelizumab
- Change in number of CD3+ T cells in CSF from treatment baseline to post-treatment with ocrelizumab

Determination of Sample Size

The sample size calculations for this study are based on the assumed reduction from baseline in NfL (Gunnarsson et al. 2011) at Weeks 24 and 52 combined (Arms 2 and 3) in the RMS cohort. Other biomarker measures are not considered for power determination.

Assuming (a) a 30% reduction from pre-treatment NfL (mean [SD] = 860 pg/mL [780 pg/mL]) to post-treatment NfL (mean [SD] = 602 pg/mL [310 pg/mL]) and a correlation coefficient of 0.6, resulting in an SD of 643 pg/mL for the change from pre- to post-treatment, and (b) a desired

power of 80% with a Type 1 error of 5%, a sample size of 51 patients is required, with approximately 25 patients in Arm 2 and 26 patients in Arm 3.

This is the first study to explore the impact of ocrelizumab on CSF B-cell count. In a study by Piccio et al. (2010), the rate of undetectable B cells in CSF was 74% (21/26) after 24–30 weeks of rituximab as an add-on to immunomodulatory therapy.

In the RMS cohort, 15 patients will be included in Arm 1 to explore the possible reduction in NfL at Week 12 post-treatment and 15 patients will be assigned to the delayed start RMS control arm (Arm 4). *At least 15 patients will be recruited to the PPMS cohort. The above sample sizes are not based on statistical considerations and are meant to help explore the changes in biomarkers and generate hypotheses for future studies.*

Based on the above, the total sample size for this study will be *at least* 96 patients. The sample size will be increased by approximately 10% in order to account for potential missing post-treatment CSF information; therefore, the number of patients to be enrolled in the RMS cohort will be 88 (Arm 1: 16 patients, Arm 2: 28 patients, Arm 3: 28 patients, and Arm 4: 16 patients), and *at least* 16 in the PPMS cohort. Therefore, the total number of patients to be enrolled is *at least* 104; *however, the addition of patients to the PPMS cohort would allow for even more detailed information on biomarkers.*

Interim Analyses

For the RMS patients, interim analysis may be performed when approximately 50% of patients have had their second LP. For the PPMS patients, interim analyses may be performed after approximately 50% of patients have had their baseline LP and/or approximately 50% have had their second LP.

APPENDIX 2
VISIT WINDOWING FOR MAIN TREATMENT AND LTE PERIOD

Visit window for vital sign and blood biomarkers (Arm 1-4 & PPMS):

Report Visit Label	Nominal study days (from baseline)	Visit window (in terms of study days from baseline)	Notes
Week -12 (Arm 4)	-84	< -14	
Baseline (Arm 1-3 & PPMS)	1	<=1	ANLFL for the record most close to day 1 if there are multiple records in the window
Baseline (Arm 4)	1	-14 - 1	Give two week window for baseline
Week 3	21	2<= and <=53	Window is from Day 2 until Week 7.5+0.5 day
Week 12	84	54<= and <=126	Window is from Week 7.5+1.5 day until Week 18
Week 24	168	127<= and <=210	Window is from Week 18+1 day until Week 30
Week 36	252	211<= and <=294	Window is from Week 30+1 day until Week 42
Week 48	336	295<= and <=350	Window is from Week 42+1 day until Week 50
Week 52	364	351 - < LTE Day 1 (if entered LTE) 351 – patient end of main study date (if not entered LTE)	Window is from Week 50+1 day until end of main study date
Week 96	672	LTE Day 1 - <=840	Window is from LTE Day 1 to Week 120
Week 144	1008	>=841 and <=1,176	Window is from Week 120+1 day until Week 168
Week 192	1344	>=1,177 and <=1,512	Window is from Week 168+1 day until Week 216
Week 240	1680	>= 1,513	Window is from Week 216 to end of LTE

Visit window for regular lab: hematology, chemistry and urinalysis (Arm 1-4 & PPMS):

Report Visit Label	Nominal study days (from baseline)	Visit window (in terms of study days from baseline)	Notes
Screening (Arm 4)	N/A	<=-92	
Screening (Arms 1-3 & PPMS)	N/A	<=-8	
Week -12 (Arm 4)	-84	-92< and <=-8	
Baseline (Arm 4)	1	-8< and <=1	
Baseline (Arms 1-3 & PPMS)	1	-8< and <=1	
Week 24	168	2<= and <=252	Window is from day 2 until Week 36
Week 48	336	253<= and <=350	Window is from Week 36+1 day until Week 50
Week 52	364	351 - <LTE Day 1 (if entered LTE) 351 – patient end of main study date (if not entered LTE)	Window is from Week 50+1 day until start of LTE
Week 72	504	LTE Day 1 - <=623	Window is from LTE Day 1 to Week 89
Week 96	672	>=624 and <=756	Window is from Week 89+1 day to Week 108
Week 120	840	>=757 and <=924	Window is from Week 108+1 day to Week 132
Week 144	1008	>=925 and <=1,092	Window is from Week 132+1 day to Week 156
Week 168	1176	>=1,093 and <=1,260	Window is from Week 156+1 day to Week 180
Week 192	1344	>=1,261 and <=1,428	Window is from Week 180+1 day to Week 204
Week 216	1512	>=1,429 and <=1,596	Window is from Week 204+1 day to Week 228
Week 240	1680	>=1,597	Window is from Week 228+1 day to end of LTE

Visit window for pregnancy (Arm 1-4 & PPMS):

Report Visit Label	Nominal study days (from baseline)	Visit window (in terms of study days from baseline)	Notes
Ocrelizumab—Genentech, Inc.			

Screening (Arm 4)	N/A	<-92	
Screening (Arms 1-3 & PPMS)	N/A	<=-8	
Week -12 (Arm 4)	-84	-91<= and <=-8	
Baseline (Arm 4)	1	-8< and <=1	
Baseline (Arms 1-3 & PPMS)	1	-8< and <=1	
Week 24	168	2<= and <=210	Window is from Week 18+1 day until Week 30
Week 36	252	211<= and <=294	Window is from Week 30+1 day until Week 42
Week 48	336	295<= and <=350	Window is from Week 42+1 day until Week 50
Week 52	364	351 - < LTE Day 1 (if entered LTE) 351 – patient end of main study date (if not entered LTE)	Window is from Week 50+1 day until start of LTE
Week 72	504	LTE Day 1 - <=623	Window is from LTE Day 1 to Week 89
Week 96	672	>=624 and <=756	Window is from Week 89+1 day to Week 108
Week 120	840	>=757 and <=924	Window is from Week 108+1 day to Week 132
Week 144	1008	>=925 and <=1,092	Window is from Week 132+1 day to Week 156
Week 168	1176	>=1,093 and <=1,260	Window is from Week 156+1 day to Week 180
Week 192	1344	>=1,261 and <=1,428	Window is from Week 180+1 day to Week 204
Week 216	1512	>=1,429 and <=1,596	Window is from Week 204+1 day to Week 228
Week 240	1680	>=1,597	Window is Week 228+1 day to end of LTE

Visit window for MRI biomarkers (Arm 1-4 & PPMS):

Report Visit Label	Nominal study days (from baseline)	Visit window (in terms of study days from baseline)	Notes
Week -12 (Arm 4)	-84	<=-28	
Baseline (Arm 4)	1	>-28 and <=1	Give a 4-week window for baseline visit

Baseline (Arm 1-3 & PPMS)	1	<=1	
Week 12	84	2<= and <=126	Window is from Day 2 until Week 18
Week 24	168	127<= and <=266	Window is from Week 18+1 day until Week 38
Week 52	364	267 - < LTE Day 1 (if entered LTE) 267 – patient end of main study date (if not entered LTE)	Window is from Week 38 +1 day
Week 96	672	LTE Day 1 - <=840	Window is from LTE Day 1 to Week 120
Week 144	1008	>=841 and <=1,176	Window is from Week 120+1 day to Week 168
Week 192	1344	>=1,177 and <=1,512	Window is from Week 168+1 day to Week 216
Week 240	1680	>=1,513	Window is from Week 216+1 day to end of LTE

*Early withdrawal, B cell monitoring and safety follow up 1 and 2 excluded from windowing

Visit window for CSF Biomarkers (Arm 1-4 & PPMS):

Report Visit Label	Nominal study days (from baseline)	Visit window (in terms of study days from baseline)	Notes
Week -12 (Arm 4)	-84	< -14	
Baseline (Arm 4)	1	-14 - 1	Give a 2-week window for baseline visit
Baseline (All patients except Arm 4)	1	<=1	
Week 12 (All patients)	84	2 - 126	
Week 24 (All patients)	168	127-266	
Week 52 (All patients)	364	267 - < LTE Day 1 (if entered LTE) 267 – patient end of main study date (if not entered LTE)	
Week 144 (All patients)	1,008	LTE Day 1 - <=1,344	Window is from LTE Day 1 to Week 192

Week 240 (All patients)	1,680	$\geq 1,345$	Window is from Week 192+1 day to end of LTE
-------------------------	-------	--------------	---

Visit window for EDSS:

Report Visit Label	Nominal study days (from baseline)	Visit window (in terms of study days from baseline)	Notes
Screening (Arm 4)	N/A	≤ -97	
Screening (Arm 1-3 & PPMS)	N/A	≤ -13	
Week -12 Pre-Baseline (Arm 4)	-84	$-97 - \leq -14$	Give a 2-week window for baseline visit
Baseline (Arm 1-3 & PPMS)	1	$-13 - \leq 1$	Give a 2-week window for baseline visit
Baseline (Arm 4)	1	$-14 - \leq 1$	Give a 2-week window for baseline visit
Week 12 (All Patients)	84	$2 \leq \text{and} \leq 126$	Window is from Day 2 until Week 18
Week 24 (All Patients)	168	$127 \leq \text{and} \leq 210$	
Week 36 (All Patients)	252	$211 \leq \text{and} \leq 294$	
Week 48 (All Patients)	336	$295 \leq \text{and} \leq 350$	
Week 52	364	$267 - < \text{LTE Day 1 (if entered LTE)}$ $267 - \text{patient end of main study date (if not entered LTE)}$	Window is from Week 38 +1 day
Week 96	672	LTE Day 1 - ≤ 840	Window is from LTE Day 1 to Week 120
Week 144	1008	$\geq 841 \text{ and} \leq 1,176$	Window is from Week 120+1 day to Week 168
Week 192	1344	$\geq 1,177 \text{ and} \leq 1,512$	Window is from Week 168+1 day to Week 216
Week 240	1680	$\geq 1,513$	Window is from Week 216+1 day to end of LTE

*Early withdrawal, B cell monitoring and safety follow up 1 and 2 excluded from windowing

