Patients in the PPMS cohort will receive an LP at the start of the study before dosing with ocrelizumab. Subsequently, they will receive a second LP at Week 52 following the first dose of ocrelizumab.

During the Long-term Extension Period, patients will be asked to consent to LPs performed every 2 years. Refer to the protocol regarding more details of study design including the long term extension period.

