4.4 EFFICACY ANALYSIS

All biomarker assessments (scheduled or unscheduled) will be summarized after applying visit windows. Summary of the visit windowing rules can be found in Appendix 2. See Module 3 for full visit window specifications. If multiple values of the same parameter occur within the same time window for blood biomarkers

Ocrelizumab—Genentech, Inc.

15/Statistical Analysis Plan ML29966

or regular lab values, the worst value for that parameter will be presented in the summary table. If multiple MRI scans occur within the same time window, the scan closest to the scheduled visit date will be included in the analysis.

All summaries will be done based on the ITT population and summaries will be provided by the actual arm, as determined by the actual timing of 2nd LP:

For patients randomized to Arm 1-3,

If the second LP date is missing then patient is included in the arm where originally randomized to;

Else:

Study Day of second LP (= date of the 2nd LP – 1st infusion start date +1)	Treatment Arm
≤126	Arm 1
127-266	Arm 2
≥267	Arm 3

Patients randomized to Arm 4 will be summarized as Arm 4 regardless of the timing of 2nd LP.

Unless otherwise specified and where appropriate, statistical tests, if any, will be performed at the two-sided 5% significance level. Corresponding 95% confidence intervals will be presented as appropriate. No corrections for multiple testing will be applied.

For biomarkers measured below the lower limit of quantification (LLOQ), numeric values will be imputed using half of the LLOQ.

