4.4.1 Primary Endpoints

For RMS cohort arm 1-3, the following values at treatment baseline and post-baseline visits, and changes and percent changes from treatment baseline to post-baseline visits will be summarized by arm:

- Levels of NfL in CSF
- Number of CD19 + B cells in CSF
- Number of CD3+T cells in CSF

The median (IQR) value at pre-treatment baseline, treatment baseline and post-baseline visits will be plotted over time and color coded by each arm. Scatter points of data will be laid over the median (IQR) plot.

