4.4.2 Exploratory Endpoints

4.4.2.1 Summaries of Exploratory Endpoints Over Time

For RMS patients in Arm 4, values at pre-treatment baseline and treatment baseline, and change and percent change from treatment baseline to post-baseline visits will be summarized.

For RMS patients in arms 1-3 and PPMS patient arm, CSF biomarker endpoints, blood biomarker endpoints and MRI biomarker endpoints stated in Section 2.2.2 will be summarized over time following the same rule as the primary efficacy endpoint, as stated in Section 4.4.1. The median (IQR) value of CSF and blood biomarkers at pre-treatment baseline, treatment baseline and post-baseline visits will be plotted over time and color coded by each arm. Scatter points of data will be laid over the median (IQR) plot for blood NfL level, CD19+ B cell and CD3+ T cell numbers.

Mean (SD) of MRI biomarker endpoints will be summarized over time.

For blood biomarkers, patient arms will also be pooled to look at the effect of ocrelizumab over time.

4.4.2.2 Comparison between Arm 1 and Arm 4

For patients in Arm 4, changes from pre-treatment baseline to treatment baseline will be compared to Arm 1 change from treatment baseline to Week 12 through an ANCOVA model adjusting for baseline DMT status (DMT naïve vs. DMT experienced) and baseline biomarker level for the following endpoints:

- CSF CD19+ B cell, CD3+ T cell and NfL
- Blood CD19+ B cell, CD3+ T cell and NfL

If data are highly skewed, ANCOVA model will be based on percent changes.

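### Extension CSF and MRI summaries are specified by arm only, with over-time pooling stated for blood alone, which costs precision at visits where the RMS arms no longer differ in exposure

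*SAP*

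**What the plan says.** SAP 4.4 sets the reporting unit for efficacy and biomarker data: "summaries will be provided by the actual arm, as determined by the actual timing of 2nd LP". A table of study-day ranges applies this rule to patients randomised to Arms 1-3. Arm 4 is exempt: "Patients randomized to Arm 4 will be summarized as Arm 4 regardless of the timing of 2nd LP".

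SAP 4.4.1 covers the CSF primary endpoints: "changes and percent changes from treatment baseline to post-baseline visits will be summarized by arm". SAP 4.4.2.1 carries this over to the CSF, blood and MRI endpoints of Arms 1-3 and PPMS, which "will be summarized over time following the same rule as the primary efficacy endpoint, as stated in Section 4.4.1". Arm 4 has its own sentence, with change taken from treatment baseline. The section then adds: "For blood biomarkers, patient arms will also be pooled to look at the effect of ocrelizumab over time". It has no matching sentence for CSF or MRI. The only other pooling statement, in SAP 4.4.2.3, is permissive and limited to baseline values in the association analyses.

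On the extension, SAP 2 says: "During the Long-term Extension Period, patients will be asked to consent to LPs performed every 2 years". In SAP Appendix 2, the table headed "Visit window for CSF Biomarkers (Arm 1-4 & PPMS") gives windows at Weeks 144 and 240 for all patients. The table headed "Visit window for MRI biomarkers (Arm 1-4 & PPMS") has common MRI windows at Weeks 12, 24, 52, 96, 144, 192 and 240. SAP 4.1.1 notes that the arms differ in the timing of the second LP but receive the same treatment. The synopsis in SAP Appendix 1 gives the RMS arms the same dosing every 24 weeks from Week 72.

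**The concern.** The arms exist to place the second LP at Week 12, 24 or 52, or, in Arm 4, before treatment starts. That grouping is needed for main-period CSF, where each arm supplies a different timepoint. It is not needed at Weeks 144 and 240, because the date of a much earlier LP says nothing about ocrelizumab exposure by then. MRI is scheduled at common times from first dose in every RMS arm, so the same reasoning applies to it throughout.

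The SAP already accepts this argument for blood and gives no reason to treat MRI or extension CSF differently. Its sample size also rests on two arms combined. At stake is the precision of the long-term estimates: as specified, the same data are reported in four small RMS groups with no overall RMS figure.

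**Working it through.** **Inputs (SAP 2.3).** Planned RMS enrolment is 16, 28, 28 and 16 in Arms 1 to 4, total 88. Pre-treatment NfL is 860 pg/mL (SD 780), post-treatment SD 310, correlation 0.6. The planned reduction is 30% of 860 = 258 pg/mL.

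**The plan's own figures.** SD of change = √(780² + 310² − 2 × 0.6 × 780 × 310) = 643.7, which the SAP gives as 643. A two-sided 5% paired t-test for 258 with SD 643 first reaches 80% power at n = 51 (power 0.802). The stated 51 patients, Arms 2 and 3 combined, is reproduced.

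**Extension CSF NfL.** No extension-entry or LP-consent rate is given, so the share of planned patients who supply a sample is an assumption, shown as a range. That the SD of 643, assumed for Weeks 24 and 52, also holds at Weeks 144 and 240 is a second assumption. The 95% half-width is t(0.975, n−1) × 643/√n. For n = 16 this is 2.131 × 643/4 = 343. Each cell below gives n, half-width in pg/mL, and power for a 258 pg/mL change.

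| Uptake | Arms 1, 4 (each) | Arms 2, 3 (each) | Arms 1-3 pooled | Arms 1-4 pooled |
|---|---|---|---|---|
| 100% | 16; 343; 0.32 | 28; 249; 0.53 | 72; 151; 0.92 | 88; 136; 0.96 |
| 50% | 8; 538; 0.17 | 14; 371; 0.29 | 36; 218; 0.65 | 44; 195; 0.74 |
| 25% | 4; 1023; 0.09 | 7; 595; 0.15 | 18; 320; 0.36 | 22; 285; 0.43 |

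The Arms 1-4 pool reaches 80% power only with 51 of 88 patients sampled, an uptake of 58%.

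**MRI.** With equal SD and full attendance, the ratio of the by-arm to the pooled standard error is √(N pooled / n arm). Against 88 this is √(88/16) = 2.3 and √(88/28) = 1.8. Against Arms 1-3 alone (72) it is √(72/16) = 2.1 and √(72/28) = 1.6.

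**The case against.** The strongest reply is that little depends on this. SAP 4 calls the analyses mostly descriptive, no paired test of extension CSF by arm is specified, and log transformation of CSF NfL is anticipated. Power and raw-scale t-intervals are therefore only a rough guide to the planned output, especially at n = 4. That stands: the figures show relative precision, not the failure of a planned test.

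A pooled mean and SD can also be rebuilt from by-arm n, mean and SD. This is true, but pooled medians and quartiles cannot be rebuilt that way, and the SAP's CSF plots show median and IQR.

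Arm 4 is not randomised, is recruited separately, stays on its current therapy or no treatment for 12 weeks before dosing, and has its own baseline windows. This also stands, and it is why Arms 1-3 should be shown pooled as well.

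Finally, SAP 4.9 places the list of outputs in Module 2, which was not available. Pooled tables may be listed there, so the supportable statement is that pooling is not stated in this SAP.

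A reader might go further in three ways that the documents do not support:
- **That each arm will hold only a handful of extension samples.** No uptake is given; at 50% the arms hold 8 to 14.
- **That extension CSF change is a principal output of the extension.** The extension rationale in SAP Appendix 1 centres on baseline CSF NfL, serum NfL and five-year brain volume.
- **That MRI also depends on optional samples.** Main-period scans at Weeks 12, 24 and 52 are scheduled for all patients in Protocol Appendices 1 to 3; for MRI the loss is precision only.

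**Conclusion.** The point holds as a loss of precision. The by-arm rule gives wider intervals than the same data support at any uptake: for extension CSF NfL, 343 or 249 pg/mL by arm against 136 pooled at full uptake, and 1023 or 595 against 285 at 25%. For MRI the by-arm standard error is about 2.3 or 1.8 times the pooled one. These sizes rest on planned enrolment, an assumed uptake, an SD of 643 carried into the extension, and, for MRI, equal SD and full attendance.

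It would be tempting to conclude that the pooled RMS sample could show the reduction on which the study was sized. At 25% uptake the pooled half-width of 285 exceeds 258 and power is 0.43; at 50% power is 0.74, still short of 80%. Nor is this a defect of error control: SAP 4.8 says that the interim analyses will not drive study conduct, and no formal conclusion depends on these summaries. It is a worthwhile, low-cost improvement that follows the SAP's own treatment of blood biomarkers.

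**What to change.** In SAP 4.4.2.1, extend the blood pooling sentence so that MRI endpoints and extension CSF endpoints (Weeks 144 and 240) are also summarised pooled over RMS Arms 1-4, by visit window from first dose, with Arm 4 change taken from its treatment baseline. Show n at each visit and the within-patient change with its 95% CI, on the log or percent scale if skewed. Show Arms 1-3 pooled alongside, because Arm 4 is non-randomised and recruited separately. Keep PPMS separate and retain the by-arm tables. Check that SAP Module 2 lists the matching outputs.

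The cost is one sentence or so in the SAP and an extra column or two in existing tables. No new data are needed.
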